4.1. Overall Design

This investigation consists of two parts;

Part 1:

- A pilot investigation with the purpose of testing the functionality of the developed dCBT-PF.
- This is a single-arm, 4-week, open investigation that will enroll 10-20 subjects with IPF. All subjects will receive dCBT-PF.

Prior to initiation of part 2, an update to the dCBT-PF will be performed, based on the provided feedback during part 1.

Part 2:

- A pivotal investigation with the purpose of evaluating the efficacy of dCBT-PF versus a control group on patient-reported psychological symptom burden in subjects with PF.
- A 9-week, randomised, assessor-blind, controlled, parallel-group clinical investigation
 evaluating the impact of dCBT-PF on psychological symptom burden in adults with PF.
 Recruitment for Part 2 will continue until end July 2023, or when a maximum of 250 subjects
 with PF have been enrolled, whatever comes first. Subjects will be randomised 1:1 to dCBTPF or an open-label control group.
- Randomization will be stratified by anxiety severity (GAD-7 score 5-9, 10-14 or >15 points) at baseline.

4.2. Scientific Rationale for Design of Clinical Investigation

The proposed clinical investigation design is based on the guidance provided by FDA, EMA and the international organization for standardization (ISO) (EU, 2017; FDA, 1996; ISO, 2020) and recently conducted DTx clinical investigations utilizing dCBT as a treatment of anxiety or depression (Carl et al., 2020; Gu et al., 2020).

Parts 1 and 2 of the investigation will enroll IPF and PF subjects, respectively, with a GAD-7 score of ≥ 5 , defined as mild to severe anxiety. PF patients, including IPF, are considered to have a level of anxiety appropriate for dCBT-PF treatment as it maps to psychological norms of a treatable level (Spitzer et al., 2006). Studies suggest that anxiety and depression significantly influence quality of life in patients with PF (Lee et al., 2017).

Part 1 will recruit patients with self-reported IPF.

Part 2 will recruit patients with self-reported PF, who have radiological findings of PF (interstitial changes) on a CT scan report, as confirmed by the PI. Historical CT scans, not older than 5 years, are used for this assessment. As most cases of PF are irreversible (Yu & Tang, 2022), this time span is considered acceptable.

dCBT-PF is not recommended for patients with active drug or alcohol addiction, history of suicidal behaviour, major depressive disorder, manic or psychotic disorders, and these patients will thus be excluded from the clinical investigation.

The overall aim of part 1 is to collect user feed-back on the functionality of the dCBT-PF from IPF patients with anxiety.

Part 2 will use the GAD-7 questionnaire to assess the primary endpoint. The GAD-7 questionnaire is considered responsive to evaluate the level of generalized anxiety disorder. The GAD-7 questionnaire has been used to assess effect on anxiety symptom severity in recently conducted CBT DTx investigations (Carl et al., 2020).

The planned dCBT-PF treatment duration is 9 weeks with an intended daily use of 10 minutes. Traditional CBT conducted via sessions with a psychologist, or a psychotherapist can vary considerably in length and duration, with sessions lasting between 30 to 60 minutes and treatment containing 5 to 20 sessions (NHS, 2019). The dCBT-PF consist of 7 interventional CBT modules (Therapy modules) and 3 non-interventional modules (PF Essentials). A target treatment duration of 9 weeks in the pivotal part of the clinical investigation is considered justifiable based on both traditional and digital CBT experience.

To minimize bias, the clinical investigation will have a randomised, assessor-blind, controlled design. Subjects will be randomised 1:1 to dCBT-PF or an open-label waitlist control group and the randomization will be stratified by self-reported anxiety severity based on GAD-7 score to ensure an equal distribution in both groups (active and control).

Implementation of a placebo-app (sham) would not provide sufficient blinding and was considered to create substantial bias in the design of the clinical investigation. A clinician-reported outcome, HAM-A, assessed by a blinded clinician, is implemented to support the primary endpoint.

The proportion of PF patients with mild to moderate anxiety (scoring 5-14 on a 0-21 scale) may be as high as 60% in patients with PF (Coelho et al., 2010; Glaspole et al., 2017; Holland et al., 2014; Lee et al., 2017). Although live sessions with a psychotherapist providing traditional CBT could be effective for PF patients, psychological therapy or other mental health interventions are not part of standard of care in patients with PF (Raghu et al., 2015).

4.3. End of Clinical Investigation Definition

End of clinical investigation is defined as the date of the last visit of the last subject. A subject is considered to have completed the clinical investigation if he/she has completed the Week 12 visit (follow-up).

5. Investigation Population

Part 1 of this clinical investigation will enroll adult subjects with IPF and mild to severe anxiety (i.e., a GAD-7 score \geq 5).

Part 2 will enroll adult subjects with PF and mild to severe anxiety (i.e., GAD-7 score \geq 5).

Prospective approval of deviations to recruitment and enrollment criteria, also known as waivers or exemptions, is not permitted.

5.1. Eligibility criteria for the Part 1, pilot phase

Subjects are eligible to be included in the investigation only if the following criteria are fulfilled:

5.1.1. Inclusion criteria (Part 1, pilot)

- 1. Age \geq 22 years at the time of signing the informed consent
- 2. Self-reported IPF diagnosis
- 3. A GAD-7 composite score of ≥ 5 at baseline (Visit 1)
- 4. If currently on prescribed medication for depression/anxiety, a stable dose for at least 4 weeks prior to baseline (Visit 1)
- 5. Capable of using a mobile device (compatible with dCBT-IPF) and common applications, in the judgement of the investigator or designee, and has an appropriate mobile or tablet device
- 6. Written informed consent, consistent with Good Clinical Practice and local laws, obtained before the initiation of any procedures related to the clinical investigation
- 7. Capable of giving signed informed consent which includes compliance with the requirements and restrictions listed in the informed consent form (ICF) and in this clinical investigation plan (CIP)

5.1.2. Exclusion criteria (Part 1, pilot)

- 1. Manic disorders, psychotic disorders, suicidal ideation, schizophrenia, self-harm, or alcohol/drug abuse during the past 6 months prior to baseline (Visit 1) as judged by the investigator or designee
- 2. Cognitive impairment e.g., dementia preventing engagement with dCBT-IPF as judged by the investigator or designee
- 3. Verbal and/or written communication problems limiting ability to engage with dCBT-IPF as judged by the investigator or designee
- 4. Inability to comply with investigation procedures, due to severe medical conditions or otherwise as judged by the investigator or designee
- 5. Life expectancy of less than 6 months as determined by the need for palliative care as judged by the investigator or designee
- 6. Currently receiving CBT

5.2. Eligibility criteria for the Part 2, pivotal phase

Subjects are eligible to be included in the investigation only if the following criteria are fulfilled:

5.2.1. Inclusion criteria (Part 2, pivotal)

- 1. Age \geq 22 years at the time of signing the informed consent
- 2. Self-reported PF diagnosis
- 3. A GAD-7 composite score of ≥ 5 at pre-screening and baseline (Visit 1)
- 4. If currently on prescribed medication for depression/anxiety, a stable dose for at least 4 weeks prior to baseline (Visit 1)
- 5. CT (Computed Tomography) within 5 years prior to baseline (Visit 1) with signs of pulmonary fibrosis (interstitial changes), as judged by the investigator or designee
- 6. Capable of using a mobile device (compatible with dCBT-PF) and common applications, in the judgement of the investigator or designee, and has an appropriate mobile or tablet device
- 7. Written informed consent, consistent with Good Clinical Practice and local laws, obtained before the initiation of any procedures related to the clinical investigation
- 8. Capable of giving signed informed consent which includes compliance with the requirements and restrictions listed in the informed consent form (ICF) and in this clinical investigation plan (CIP)

5.2.2. Exclusion criteria (Part 2, pivotal)

- 1. Self-reported manic disorders, psychotic disorders, schizophrenia, or alcohol/drug abuse during the past 6 months prior to baseline (Visit 1), as judged by the investigator or designee
- 2. Self-reported history of hospital admissions due to suicidal behavior or attempts, as judged by the investigator or designee
- 3. Self-reported previous or current diagnosis of major depressive disorder, as judged by the investigator or designee
- 4. Verbal and/or written communication problems limiting ability to engage with dCBT-PF as judged by the investigator or designee
- 5. Inability to comply with investigation procedures, due to e.g. cognitive impairment or severe medical conditions as judged by the investigator or designee
- 6. Currently receiving CBT
- 7. Participation in the pilot phase of the clinical investigation

5.3. Lifestyle Considerations

There are no lifestyle considerations in the investigation.

5.4. Screen Failures

A screen failure occurs when a subject who consents to participating in the clinical investigation is not subsequently randomly assigned to dCBT-PF or the control group.

A minimal set of screen failure information is required to ensure transparent reporting of screen failure subjects to meet the Consolidated Standards of Reporting Trials publishing requirements. Minimal information includes demography, screen failure details, eligibility criteria, and any SAEs.

Re-prescreening/re-screening is allowed for the following screen failure reasons -

- Inclusion criterion 4: If stable dose is confirmed
- Inclusion criterion 5: If a CT scan report becomes available
- Inclusion criterion 6: If the subject obtains an appropriate mobile or tablet device
- Exclusion criterion 2: Subjects who pre-screen failed due to PHQ-9 question 9 under CIP V4.0, and were otherwise eligible, can be re-prescreened.
- Exclusion criterion 3: Subjects who pre-screen failed due to PHQ-9 composite score under CIP V4.0, and were otherwise eligible, can be re-prescreened.
- Exclusion criterion 6: If no longer receiving CBT

For subjects that will be re-(pre)screened all assessments will be redone. The subject ID under which the subject was previously re-(pre)screened will be recorded as part of the clinical database.

5.5. Subject reimbursement

For the pilot and pivotal phases, subjects will receive \$100.00 and \$250.00, respectively, as compensation at the completion of their participation in the investigation.

6. Investigational Medical Device

The investigational device is the dCBT-PF. dCBT-PF will be used by the subject according to the CIP.

Note - For the pilot phase, the investigational device was referred to as dCBT-IPF, as it was initially intended to IPF patients only. In the months leading up to the final product, through patient interviews and discussions with expert pulmonologists, in addition to a suggestion by FDA at a pre-submission meeting on March 21, 2022, Vicore Pharma and Alex Therapeutics decided to expand the availability of the product to patients with PF. This change was implemented prior to initiating the pivotal phase and is reflected in the CIP version 4.0. Consequently, throughout the CIP the investigational device name is changed to dCBT-PF.

6.1. Description of Medical Device

In part 1 (pilot investigation) each subject will receive dCBT-PF.

In part 2 (pivotal investigation) each subject will be randomised to receive treatment with dCBT-PF or be allocated to the control group.

The dCBT-PF device is a stand-alone digital CBT intervention, used without clinician supervision, delivered as a mobile phone or tablet (Android or iOS) application.

Subjects will, prior to use, receive instructions on how to download and use the dCBT-PF.

The dCBT consists of 7 interventional CBT modules (therapy modules) and 3 non-interventional modules (IPF essentials). The therapy modules are CBT or ACT-based digital therapy. The IPF essentials are educational material related to IPF. The therapy modules take 9 weeks to complete if used as intended. An overview of the modules is presented in Table 3. During the intervention period, the subjects will be instructed to use the dCBT-PF for approximately 10 minutes per day for an estimated time of 4 weeks in the pilot investigation and 9 weeks in the pivotal investigation.

Subjects assigned to dCBT-PF therapy in part 1 (pilot investigation) will use 4 of the modules.

In part 2 (pivotal investigation) the subjects will complete all modules. This intervention corresponds to approximately 14 face-to-face sessions with traditional CBT. The therapy modules of the dCBT-PF focus on psychoeducation and introduces concepts and ideas from CBT and ACT through text, video, and audio.

The IPF essential modules focus on educational aspects for IPF patients.

Table 3 Therapy modules

Module		Content		
1	Intro and motivations	(Barlow, 2014; Harris, 2019; Miller, 2013).		
2.	Why am I feeling like this?	Psychoeducation (Barlow, 2011; Barlow, 2002, 2014; Harris,		

[figure not shown]
[figure not shown]

Table 4 IPF essentials modules

6.2. Preparation, Handling, Storage, and Accountability

Subjects randomised to the dCBT-PF will receive a unique product code. This product code gives access to the dCBT-PF. Subjects will download an app and use the dCBT-PF on their own mobile or tablet device.

Subjects will receive instructions on how to download the dCBT-PF app from written instructions and/or via a virtual onboarding session with the site staff.

Access to the dCBT-PF will be revoked after the subject has completed the clinical investigation.

The number of days the dCBT-PF has been accessed, the time spent, and the number of modules completed will be logged in the dCBT-PF system and will be transferred to the database for the clinical investigation.

6.3. Measures to Minimize Bias: Randomization

This is a randomised, assessor-blind, controlled, parallel-group, clinical investigation. Subjects, care providers, investigators, sponsor, and CRO/vendor staff know if the subject is randomised to dCBT-PF or the control group. The control group is implemented to serve as a baseline for determining the effectiveness of the intervention. The control group will not receive any treatment but will follow the same assessment as the group randomised to dCBT-PF. Subjects in the control group will receive access to dCBT-PF treatment after the follow-up visit at Week 12 (see Section 6.5).

The clinician assessing rating anxiety based on the HAM-A questionnaire will be blinded to treatment to reduce reporter bias.

Randomization will be stratified by: Anxiety severity (GAD-7 score 5-9, 10-14 or >15 points) at baseline to prevent imbalance in anxiety level between the dCBT-PF and control group.

6.4. Investigational Device Compliance

Subjects randomised to the dCBT-PF will receive access to the dCBT-PF app. Adherence to the dCBT-PF will be measured in terms of the number of days the dCBT-PF app is accessed, time spent, and the number of modules completed during the treatment period.

Adherence to the dCBT-PF will be assessed by a weekly compliance report prepared by Alex Therapeutics. The reports will indicate the compliance adherence by color coding. If compliance is less than expected, the site staff should discuss the reason and educate the subject to comply with the investigation. Intervention start and stop dates will also be recorded in the dCBT-PF database and will be transferred to the database for the clinical investigation.

6.5. Continued Access to the Investigational Device after End of the Clinical Investigation

Subjects allocated to the control group will receive access to the dCBT-PF when their participation in the investigation is completed, i.e., after the end of the 3-week follow-up period.

Access for the control group will be provided under an Exclusive Release of the product, following the FDA medical device enforcement discretion guidelines i.e., outside of the scope of this CIP. Obtaining subject consent, as well providing instructions for getting access to the dCBT-PF treatment, will be performed under this CIP, to allow for the GAD-7 data, collected through the dCBT-PF by Alex Therapeutics, the Legal Manufacturer of the product, to be used for quality control purposes and for the patient's own insight. The data collected will be anonymized.

6.6. Prior and Concomitant Therapy

Concomitant therapy is defined as any therapy (including over-the-counter, prescription medicines, oxygen supplementation, recreational drugs, vitamins, treatment from a psychologist or psychiatrist and/or herbal supplements) or other specific categories of interest that the subject is receiving or continues at the time of enrollment or receives after start of treatment with the dCBT-PF.

All concomitant therapy taken according to the subject at baseline (Visit 1) should be recorded. In addition, relevant prior therapy taken up to 4 weeks prior to baseline (Visit 1) should be recorded. Relevant prior therapy is defined as antifibrotic treatment, psychological therapy including counseling, antidepressants, or anti-anxiety treatments. Other relevant prior therapy can be reported at investigator's discretion.

Concomitant therapy and prior therapy must be recorded along with:

- Reason for use
- Dates of administration including start and end dates
- Dosage information including dose and frequency

7. Discontinuation of Investigational Medical Device and Subject Discontinuation/Withdrawal

Discontinuation of the clinical investigation is detailed in Appendix 1 (see Section 10.1).

7.1. Discontinuation of Investigational Medical Device treatment

A subject should be discontinued from the dCBT-PF if, in the opinion of the investigator it is medically necessary or if it is the wish of the subject.

If treatment with dCBT-PF is discontinued, the investigator or designee should make all efforts to ensure that the subject will remain in the clinical investigation and ensure that the subject attends the remaining visits.

7.1.1. Temporary Discontinuation

There are no specific criteria for temporary discontinuation of dCBT-PF treatment. If a temporary discontinuation is required according to the investigator's judgement, the stop and start date and reason for a temporary discontinuation should be reported in the case report form (CRF). If the subject is still within the treatment period of the clinical investigation when a temporary discontinuation is no longer required, treatment with the dCBT-PF can be restarted.

7.2. Subject Discontinuation/Withdrawal from the Clinical Investigation

- A subject may withdraw from the clinical investigation at any time at his/her own request i.e., withdrawal of consent.
- Subjects expressing significant new or worsened negative wellbeing or distress during the study will be withdrawn from the clinical investigation (cf. separately IRB approved 'Suicide Ideation Process').
- The subject will be permanently discontinued from using the dCBT-PF at the time of withdrawal from the clinical investigation.
- If the subject withdraws consent for disclosure of future information, the sponsor may retain and continue to use any data collected before such a withdrawal of consent.

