2.3.3. Overall Benefit Risk Conclusion

The overall benefit risk balance is considered positive. This is based on the consideration that none, or a limited number of, ADEs are expected using dCBT, the virtual nature of the clinical investigation and potential benefits in treating anxiety with dCBT.

3. Objectives, Endpoints, and Estimands

[figure not shown]
Pilot investigation – Part 1:

Objectives	Endpoints
Primary	
To evaluate the functionality of dCBT-PF in patients with IPF	Subjects feedback on functionality and experience of the dCBT-PF at Week 4
Safety	
To evaluate the safety of dCBT-PF in patients with IPF	AEs, ADEs, SAEs, SADE and device deficiencies which could lead to an ADE or SADE

Pivotal investigation – Part 2:

Objectives	Endpoints
Primary	
To evaluate the efficacy of dCBT-PF versus control on patient-reported anxiety symptoms in patients with PF	Change from baseline in anxiety symptom severity assessed by GAD-7 at Week 9
Key secondary	
To evaluate the efficacy of dCBT-PF versus control on clinician-reported anxiety symptoms in patients with PF	Change from baseline in anxiety symptom severity as assessed by Hamilton anxiety rating scale (HAM-A) at Week 9
To evaluate the efficacy of dCBT-PF versus control on patient-reported health-related quality of life (HRQoL) in patients	Change from baseline in HRQoL assessed by K-BILD psychological domain score at Week 9
with PF	Change from baseline in HRQoL assessed by K-BILD total score at Week 9

Safety	
To evaluate the safety of dCBT-PF versus control in patients with PF	AEs, ADEs, SAEs, SADEs and device deficiencies which could lead to an ADE or SADE

Primary Estimand:

The change from baseline to Week 9 in GAD-7 scores, assessed for the intention-to-treat population with treatment as randomised, independent of treatment withdrawal or major deviations according to the treatment policy, with withdrawals from the clinical investigation prior to Week 9 not possible to follow-up being imputed using multiple imputation including their last known assessment. The difference between treatments with 95% confidence intervals from ANCOVA adjusting for stratification will be estimated.

Key Secondary Estimands:

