9.3.2. Primary Endpoint/Estimand Analysis

The primary endpoint, change from baseline in patient-reported anxiety symptom severity assessed by GAD-7 at Week 9, will be compared between treatment groups using an ANCOVA model with treatment and strata (baseline anxiety severity) as factors, the baseline GAD-7 score as covariate and the baseline by strata interaction.

The adjusted mean difference between groups will be given together with 95% confidence intervals and associated 2-sided p-value.

Withdrawals prior to Week 9 not possible to follow-up will be imputed using multiple imputation taking subjects baseline characteristics, treatment, and post-treatment GAD-7 scores into account.

The ITT analysis set will be used for the main analysis of the primary endpoint. Sensitivity analyses will be performed with alternative methods for imputation (for instance using the average of the opposite treatment group as base) and a tipping point analysis will also be performed investigating the impact on the treatment effect by successive shifts introduced in the imputation for the active group. Sensitivity analysis will be described in the SAP. In all analyses subjects will be included as randomised. All collected data post-intervention will be used to assess the endpoint.

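### Section 7.2 removes distressed subjects in either arm from the investigation and provides for no Week 9 assessment afterwards, which works against the treatment-policy estimand

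*Combined protocol and SAP*

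**What the plan says.** Section 7.2 sets the consequence of a distress trigger: "Subjects expressing significant new or worsened negative wellbeing or distress during the study will be withdrawn from the clinical investigation". It refers to a separately approved Suicide Ideation Process, which is not part of the document. The bullet is mandatory, does not distinguish arms, and concerns the investigation rather than the device.

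The rule reaches both arms. Section 6.3 gives controls the same assessments as the dCBT-PF group. Table 2 in Section 1.3 schedules the distress question at V2 to V5 without arm restriction, with a footnote pointing to Sections 2.3.1 and 7.2.

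Section 7.1 covers a different event. When only the device is stopped, site staff "should make all efforts to ensure that the subject will remain in the clinical investigation and ensure that the subject attends the remaining visits".

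The primary estimand in Section 3 takes the Week 9 change in GAD-7 "independent of treatment withdrawal or major deviations according to the treatment policy". For values missing at Week 9 it provides for "withdrawals from the clinical investigation prior to Week 9 not possible to follow-up being imputed using multiple imputation". Under Section 9.3.2 these values are "imputed using multiple imputation taking subjects baseline characteristics, treatment, and post-treatment GAD-7 scores into account". That section also says that all data collected after the intervention are used. Its sensitivity analyses are alternative imputations, "for instance using the average of the opposite treatment group as base", and a tipping point with "successive shifts introduced in the imputation for the active group".

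**The concern.** A treatment-policy estimand needs the Week 9 value whatever happened to treatment. A subject withdrawn by rule may be reachable and willing, so this loss is created by the protocol, and its trigger lies close to the construct that GAD-7 measures. In the control arm there is no device to stop, so withdrawal ends the scheduled assessments without removing any exposure.

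The imputation model sees the subject's earlier GAD-7 scores. Distress and GAD-7 are both assessed at V2 and V3, so part of the worsening should already be in those scores. Whatever part is not is lost, and reason for withdrawal is not among the listed imputation inputs. The error favours dCBT-PF if the device raises distress, which is the risk named in Section 2.3.1. It goes against dCBT-PF if an effective device lowers distress. Week 9 HAM-A, the blinded outcome meant to support the primary endpoint, and K-BILD are lost in the same subjects.

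**Working it through.** **Is there a retention rule for these subjects?** Four places could supply one.

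- Section 7.1 asks for retention, but only after device discontinuation.
- Section 7.2, beyond the trigger bullet, says only that device use ends at withdrawal and that data collected before a withdrawal of consent may be kept.
- Section 7.3 requires repeated contact attempts, but for missed visits and lost contact.
- Section 8.4.3 continues follow-up of SAEs and SADEs, not of efficacy questionnaires.

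None asks for GAD-7, HAM-A or K-BILD at Week 9 after a distress withdrawal. Section 9.3.2 would use such data but does not cause them to be collected.

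**Inputs for the size.** From the document: a maximum of 250 subjects randomised 1:1, so 125 per arm at the maximum. Everything else is assumed, because the available text gives no trigger rate, SD or effect size:

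- share withdrawn for distress before Week 9: 0% to 8% per arm
- excess in the Week 9 score of these subjects: 4 to 6 points
- SD 4, treatment effect 2 points

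**Formula.** Let pA and pC be the shares withdrawn on dCBT-PF and control, and d the number of points by which imputation understates their Week 9 score. For the difference dCBT-PF minus control,

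bias = −(pA − pC) × d, where a negative value favours dCBT-PF.

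**Simulation.** 1,500 trials were simulated with 125 per arm, SD 4, adjacent-visit correlation 0.7, and an effect of −2 in subjects without an episode. Triggered subjects were missing at Week 9, and 10 imputations used baseline, arm, V2 and V3. The last two columns give the imputed minus the full-data estimate.

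| pA vs pC | Excess | Outcomes lost | Formula, d = full excess | Simulated, none visible earlier | Simulated, half visible at V3 |
|---|---|---|---|---|---|
| 8% vs 0% | 6 | 10 | −0.48 | −0.49 | −0.31 |
| 8% vs 0% | 4 | 10 | −0.32 | −0.32 | −0.21 |
| 4% vs 0% | 4 | 5 | −0.16 | −0.16 | −0.11 |
| 4% vs 4% | 4 | 10 | 0 | 0.00 | 0.00 |
| 4% vs 8% | 6 | 15 | +0.24 | +0.24 | +0.15 |
| 0% vs 8% | 6 | 10 | +0.48 | +0.48 | +0.31 |
| 1% vs 0% | 4 | 1.25 | −0.04 | −0.04 | −0.03 |
| 1% vs 0% | 6 | 1.25 | −0.06 | −0.06 | −0.04 |

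The half-visible column follows from the correlation. Of the 3 points seen at V3, 0.7 × 3 = 2.1 carry into the imputed value, so d = 6 − 2.1 = 3.9 and 0.08 × 3.9 = 0.31. If the visible half carried forward in full, the result would be 0.08 × 3 = 0.24.

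**Scale.** The simulated standard error of the difference is 0.48 to 0.49, so the largest shift is about one standard error. Against the assumed 2-point effect it is 0.48 / 2 = 24%.

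**Effect of the planned opposite-group imputation.** Switching the arm term for triggered subjects, with no excess visible earlier, gives −0.40 for 8% versus 0% at 6 points (−0.49 under the main method). For 0% versus 8% it gives +0.57 (+0.48 under the main method). It moves the estimate against dCBT-PF in both cases and removes little of the bias in the first.

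**Timing.** Only triggers before the Week 9 GAD-7 matter for the primary endpoint. A trigger at V4 after GAD-7, or at V5, does not.

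**The case against.** The strongest reply is that the plan already anticipates follow-up. The estimand imputes only withdrawals that cannot be followed, Section 9.3.2 uses whatever is collected, and the Suicide Ideation Process may contain contact rules. On that view only an operational sentence is missing. This is fair as far as it goes: Section 7.2 does not forbid later follow-up and does not literally contradict 7.1. But intent without a procedure yields no data, and 7.2 as written states withdrawal as the outcome. If the separate process does keep the assessments, 7.2 should say so.

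Second, the upper figures are pessimistic. An excess of 6 points is 1.5 SD at SD 4, and 0.48 requires that none of it shows at V2 or V3, although GAD-7 has a two-week recall. Section 2.3.3 expects few or no ADEs, and the trial excludes prior admissions for suicidal behaviour and major depressive disorder. This stands: the rare-trigger case is plausible, and there the shift is about a tenth of a standard error. The ADE expectation does not, however, bound distress arising from the disease itself in either arm.

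Third, the active-group tipping point tests the direction that would flatter dCBT-PF, and a bias in the other direction is conservative for superiority. That is correct. The tipping point still measures sensitivity to values that could have been observed, and it leaves control withdrawals unshifted.

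Finally, the rule protects participants. A revised rule must keep that protection, and the most distressed subjects may still decline, so not every value would be recovered.

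**Conclusion.** The concern holds. As written, Section 7.2 produces avoidable, outcome-related missing Week 9 data in both arms under an estimand that calls for those data. The size and direction of any bias cannot be fixed from the document. It is zero if rates and unpredicted excess match between arms. Within the assumed ranges it reaches at most 0.48 points either way, or 0.24 to 0.31 if half the excess is visible at V3. These figures treat every triggered subject as missing at Week 9. The recommendation does not rest on the worst case: the loss is preventable at little cost and falls on the one residual risk that Section 2.3.1 identifies. It is a change that should be made, not a flaw that invalidates the design. Confidence is medium, because the Suicide Ideation Process could not be read.

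**What to change.** Keep the trigger in the second bullet of Section 7.2 and its reference to the Suicide Ideation Process, and replace the consequence with wording such as:

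> The subject stops dCBT-PF, if assigned to it, and is referred for care. Unless consent is withdrawn or further contact is judged unsafe, the subject stays in the investigation and is asked for the Week 9 assessments, or for GAD-7 alone if that is all the subject accepts.

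Record the trigger date in the CRF. The analysis needs no change: Section 9.3.2 already uses all collected data, and Section 9.3.5 already reports withdrawals with reasons by group.

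The cost is a CIP amendment with IRB approval and alignment with the separately approved process. No visit is added, since Week 9 is remote and already scheduled. The downside is some burden on a distressed subject, who remains free to decline.
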